3.8 Randomization and Stratification

A separate randomization sequence will be created for each site. Within site, we will create four strata by crossing sex (male, female) and age (12-14 years, 15-17 years) and we will use permuted blocks within each stratum to ensure the three intervention conditions are balanced. A statistician in the Children's Hospital Colorado's Biostatistics Core, other than the study lead statistician [name], will create the computerized randomization sequence and enter the sequence into REDCap's randomization module. The randomization sequence will be created in randomly permuted blocks stratified by site, sex, and age. Permuted blocks will be restricted so that for each cohort of $n=15$, the conditions will be balanced. REDCap's randomization module conveniently conceals the randomization sequence. The lead research coordinator will be responsible for using the REDCap randomization module to carry out randomization of eligible participants.

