- i. Pubertal staging: As puberty is related to insulin resistance,¹⁸ Tanner staging for breast and pubic hair (females) and testicular volume and pubic hair (males) will be performed by a trained medical provider. To accommodate medical provider schedules and participant/family schedules, pubertal staging may be carried out at screening visit 1 instead. Additionally, Tanner stage will be collected through adolescents' self-report on a validated questionnaire.¹⁶² Participants will be asked to define their physical development based on illustrations of their external characteristics, which corresponded to Tanner stages 1-5 of breast and pubic hair development for girls and Tanner stages 1-5 of testicular volume and pubic hair development for boys.
- ii. Body composition: During a fasted state, fat/fat-free mass will be assessed via air displacement plethysmography (BodPod), which shows good test-retest reliability and convergence with dual energy x-ray absorptiometry,¹⁶³ but is far more cost-effective.
- iii. Stress-related behavior: Several measures of hedonic eating, referring to eating for reward/pleasure as opposed to physiological hunger,⁷⁵ will be collected. The overeating section of the Eating Disorder Examination (EDE), a semi-structured interview, will be administered by a trained research assistant to identify frequency of 3 types of eating episodes: objective binge (overeating with loss of control), subjective binge (loss of control without objective overeating as assessed by the interviewer, but viewed as excessive by the interviewee), and objective overeating (overeating without loss of control). Tests of the EDE's discriminant validity, internal consistency, concurrent validity and test-retest reliability support its use in adolescents.¹⁶⁴⁻¹⁶⁶ The EDE may be conducted in-person during the screening visit, or alternatively, may be conducted remotely using secure video software or by phone.

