8.6 Data Analyses

8.6.1 Primary Analyses

In Aim 1, descriptive analyses will be conducted to: (i) describe post-training knowledge/competency of MBI, CBT, and HealthEd to determine if facilitators score $\geq 80\%$; (ii) describe adherence and competence ratings of mock group sessions of MBI, CBT, and HealthEd to determine if ratings ≥ 8 (1-10 scale with 10 being the most positive valence); and (iii) describe adherence and competence ratings of pilot group sessions of MBI, CBT, and HealthEd by blinded, expert reviewers to determine if ratings ≥ 8 . Chi-square analyses will be used to explore whether the percentages meeting these criteria vary across conditions (MBI vs. CBT vs. HealthEd) and site. In Aim 2, study flow will be described according to CONSORT guidelines for the reporting of clinical trials.^{176,177} Descriptive analyses will be generated to determine: (i) the percentage of adolescents who enroll after being determined to be eligible, (ii) number of months to reach recruitment goal, (iii) percentage of adolescents who attended 5 of 6 ($\geq 80\%$ sessions), (iv) percentage of adolescents whose likability/credibility ratings were ≥ 4 (1-5 scale, with 5 being the most positive valence), (v) percentage of adolescents who complete post-treatment and 1-year follow-up assessments, and (vi) percentage compliance with standardized operating procedure checklists for all assessments. Analyses of variance (ANOVA) and chi-square will be used to describe any potential differences across the 4 sites and the 3 intervention arms. A Tukey adjustment will be used to control for multiple comparisons. For the primary analyses in Aims 1 and 2, we do not plan to adjust for covariates as our interest is in estimating measures of success independent of participant characteristics.

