Another purpose of secondary analyses is to supplement the mixed-methods analyses in Aim 3 used to refine study procedures and interventions in preparation for a future efficacy trial by understanding predictors associated with study outcomes, as well as mediators and moderators of intervention effects. This study is not designed as an efficacy study, and we will not necessarily have sufficient statistical power for the secondary analyses. However, results of these analyses may help inform changes to the interventions. We will examine predictors of participant attrition, attendance, and likability/credibility ratings. We will use multilevel mixed-effects models to examine change over time in measures of depression, insulin resistance, stress-related behavior, and stress physiology. These models will allow us to account for and estimate the correlation within study site and intervention cohort, as well as the correlation between repeated measures within a participant. ICC will be estimated using the method of Donner¹⁷⁹ for continuous variables and Ridout¹⁸⁰ for binary variables. The models will contain terms for group, time, and a group by time interaction. We will adjust for the baseline value of the outcome, and will also consider adjustment for baseline age, sex, race/ethnicity, particularly if these variables are not balanced across study groups. Models will be adjusted for baseline adiposity and change in adiposity to examine whether decreases in depressive symptoms improves insulin sensitivity independent of adiposity. If we find significant between-group differences in the insulin resistance, stress-related behavior, and stress physiology outcomes, we will test whether those effects are moderated by baseline depressive symptom severity (CES-D score) by including an interaction term in the model. We will also examine participant characteristics associated with these outcomes in order to better understand factors that moderate the response to intervention. Mediation analyses, using the product-of-coefficients method and bootstrapped standard errors, will be used to explore whether improvements in insulin sensitivity (if present) are mediated by changes in stress-related behaviors and stress physiology. Quantitative measures of group cohesion, therapeutic alliance, and perceived credibility/expectancy, summarized by intervention arm, will inform modifications to facilitator training, optimization of interventions, and study design in the larger trial. Finally, we will examine theoretical therapeutic mechanisms to explore the hypotheses that in MBI, mindfulness, monitoring/acceptance, and executive function will improve and in CBT, thoughts and pleasant activities will improve, compared to each other and to HealthEd.

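### Sex and age group are randomization strata, but the secondary outcome models leave adjustment for them optional; if they are omitted, the reported standard errors and intervals are too wide

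*Combined protocol and SAP*

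**What the plan says.** **Allocation.** Section 3.8 states: "The randomization sequence will be created in randomly permuted blocks stratified by site, sex, and age". Each site has four strata, sex crossed with two age bands (12-14 and 15-17 years), and section 4.3 repeats this. Four sites therefore give 16 strata.

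**Secondary outcome models.** Section 8.6.2 describes mixed models for depression, insulin resistance, stress-related behavior and stress physiology. Its commitments are definite on these points:

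- Fixed terms: "The models will contain terms for group, time, and a group by time interaction".
- Baseline: "We will adjust for the baseline value of the outcome".
- Clustering: the models will "account for and estimate the correlation within study site and intervention cohort", so one of the three stratification factors, site, is represented.
- Adiposity at baseline and its change are added, to ask whether an effect on insulin sensitivity is independent of adiposity.

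On sex and age it is not definite. The team "will also consider adjustment for baseline age, sex, race/ethnicity, particularly if these variables are not balanced across study groups". No criterion for imbalance is given, nor any rule or time for the decision. The text names age, not the age band used as a stratum. No other section commits sex or age group to these models.

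**Primary analyses.** Section 8.6.1 does make a definite choice for Aims 1 and 2, with a reason: "we do not plan to adjust for covariates as our interest is in estimating measures of success independent of participant characteristics".

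**The concern.** When allocation is blocked within strata, the arms are forced to be alike on the stratifying factors. The estimated treatment difference then varies less from trial to trial than under simple randomization. A model without those factors does not know this. It leaves their variance in the residual and reports a standard error that is too large for the estimate it accompanies.

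The wording in section 8.6.2 points towards that outcome, because its main stated prompt for adjustment is an imbalance that the design exists to prevent. The same section looks for a signal on depression and insulin sensitivity by means of one-sided 80% confidence intervals, in a sample that will be about 28 to 34 per arm after attrition. An interval wider than it needs to be makes a real signal somewhat harder to see.

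**Working it through.** **1. The plan's own figure.** The only figure stated for these analyses is a detectable effect of 0.3 SD. It can be neither confirmed nor refuted, because power, final sample size and baseline correlation are not given. With 40 per arm randomized, the 15% loss in section 8.2 leaves 34 and the 70% retention floor leaves 28.

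- Confidence-interval criterion, z(0.80) × √(2/n) with z = 0.8416: 0.225 at n = 28 and 0.204 at n = 34. An effect of 0.3 needs 2 × (0.8416/0.3)² = 15.7, so 16 per arm.
- 80% power at one-sided 0.20, 2 × 0.8416 × √(2/n): 0.45 at n = 28 and 0.41 at n = 34. An effect of 0.3 would need 63 per arm without help from the baseline value.

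Neither result decides the present point. They show how much rests on the residual variance.

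**2. How often would imbalance prompt adjustment?** Inputs from the documents: N = 120, three equal arms, 16 strata (120/16 = 7.5 adolescents each on average). Assumptions: blocks of 3, and imbalance declared when a chi-square test for sex or for age group has p < 0.10. In simulations of 4,000 trials per scenario, this rule fired in 0% to 0.2% of trials under stratified blocks. Under simple randomization it fired in 19%, as expected for two tests at 10% (1 − 0.9² = 0.19). Larger blocks would leave more incomplete blocks and raise the first figure somewhat.

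**3. What does omission cost?** The same simulations compared an analysis of covariance on baseline and site, with and without sex and age group, as a stand-in for the mixed model. Further assumptions: baseline correlation 0.5, 20% missing (32 per arm), and R² as the share of variance left after baseline that sex and age explain. The expected ratio of reported standard errors is 1/√(1 − R²).

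| R² | Reported SE, without / with | Ratio (formula) | True spread of estimate, without / with | Ratio |
|---|---|---|---|---|
| 0.05 | 0.2195 / 0.2145 | 1.02 (1.03) | 0.2190 / 0.2180 | 1.00 |
| 0.10 | 0.2188 / 0.2082 | 1.05 (1.05) | 0.2127 / 0.2092 | 1.02 |
| 0.20 | 0.2189 / 0.1962 | 1.12 (1.12) | 0.2031 / 0.1967 | 1.03 |
| 0.30 | 0.2198 / 0.1840 | 1.19 (1.20) | 0.1944 / 0.1845 | 1.05 |

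At R² = 0.20 the reported SE is 12% larger without the strata, yet the estimate itself is only 3% more variable. Most of the gap is overstatement: 0.2189/0.2031 = 1.08. At R² = 0.10 the overstatement is 0.2188/0.2127 = 1.03.

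**4. Effect on the one-sided 80% limit.** It lies 0.8416 × SE from the estimate. At R² = 0.10 that is 0.184 without the strata and 0.175 with them. At R² = 0.20 it is 0.184 and 0.165.

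**5. Error rates and power.**

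| R² | One-sided 20% error, without / with | Two-sided 5% error, without / with | Power at 0.3 SD (one-sided 0.20), without / with |
|---|---|---|---|
| 0.10 | 19.3% / 20.0% | 4.1% / 5.0% | 69.8% / 71.8% |
| 0.20 | 17.9% / 19.8% | 3.8% / 5.3% | 72.0% / 75.7% |
| 0.30 | 16.2% / 19.1% | 2.9% / 5.3% | not run |

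Simulation error is about √(0.2 × 0.8/4000) = 0.6 points for the 20% rates and 0.3 points for the 5% rates. The 19.3% is therefore not distinguishable from 20% by itself; 17.9% and 16.2% are.

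**6. Cost if sex and age are not prognostic.** At R² = 0 the reported SE is 0.2189 with the two terms and 0.2181 without, a difference of 0.4%.

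**The case against.** The best defense is that the sentence leaves adjustment to judgment. It does not make imbalance a condition, so a careful analyst could include sex and age in every model and stay within the plan. These are also secondary analyses in a pilot that section 8.6.2 says is not designed as an efficacy study and may lack power for them. Any error from omission is conservative, and its size depends on shares of variance that the documents do not supply. All of this stands, and it limits the weight of the point. It does not turn the sentence into a specification.

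Some stronger readings are tempting, but the documents do not support them:

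- *That the strata enter only if imbalanced.* The text says adjustment will be considered, particularly in that case. Adjustment without imbalance is allowed.
- *That all three strata are ignored.* Site is accounted for as a clustering level. Making it a fixed effect instead would sit badly with the stated aim of estimating correlation within site.
- *That omission throws away a matching share of the sample.* The factor 1/√(1 − R²) describes the reported standard error. The blocking has already secured most of the precision in the estimate.
- *That leaving out pubertal stage is part of the same error.* Section 6.2.4 collects it with the remark "As puberty is related to insulin resistance", so it is a sensible optional covariate for the insulin outcomes. It is not a stratification factor, and nothing in the design obliges its use.

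**Conclusion.** The point holds in a limited form. Two of the three stratification factors have no committed place in the secondary models, and the main stated prompt for including them will almost never arise under the planned allocation. If they are omitted, the treatment effect is not biased and false positives do not increase. The loss is in the reported uncertainty: standard errors and one-sided 80% limits about 2%, 5% or 12% wider than in the adjusted model for R² of 0.05, 0.10 or 0.20, and about 2 to 4 points of power at 0.3 SD for R² of 0.10 to 0.20.

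These sizes rest on the assumed R², blocks of 3, a baseline correlation of 0.5, 20% missing data and a single follow-up without therapy-group clustering. They also take the one-sided intervals to come from the mixed models, which section 8.6.2 implies but does not say outright. The primary fidelity and feasibility analyses are unadjusted by a stated choice and are not touched. This is a correction worth making because it is nearly free. It is not a threat to the trial's conclusions.

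**What to change.** In section 8.6.2, replace the sentence on considering adjustment with a commitment: all secondary treatment-effect models, including those that produce the one-sided 80% intervals, contain sex and age group (12-14, 15-17 years) as covariates. These stand beside the baseline value of the outcome and the site and cohort terms already planned, whatever balance is observed. Move race/ethnicity to a named sensitivity analysis, so that no covariate in the main models depends on a look at the baseline table. Settle the wording before the statistician is unblinded at database lock.

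The cost is about 2 degrees of freedom out of roughly 90, and a change of SAP wording. The variables are already collected. Baseline Tanner stage may be added for the insulin outcomes if the team wishes, provided this is fixed at the same time.

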regardless of their valence, mechanisms supported in recent MBI dismantling studies.^{65,67-69} As show in **Figure 1** below, MBI is theorized to be particularly fitting for decreasing depression and improving insulin resistance in teen at-risk for T2D. MBI is postulated to: (a) alleviate ruminative, negative thoughts that perpetuate and exacerbate depression,⁷⁰⁻⁷² (b) ameliorate dysregulated stress physiology including cortisol dysregulation and stress reactivity, shown to promote insulin resistance and adverse metabolic outcomes,^{73,74} and (c) lessen stress-related behavior such as hedonic eating, or eating for reward/pleasure as opposed to physiological hunger,⁷⁵ and physical inactivity.⁷⁶ Adolescent depression symptoms relate to increases in cortisol dysregulation,^{77,78} stress reactivity,⁷⁹ hedonic eating,⁸⁰⁻⁸² and physical inactivity,⁸³ which, in turn, have each been related to increased insulin resistance independent of obesity.⁸⁴⁻⁹⁷ Enhanced monitoring and acceptance of thoughts, emotions, and body sensations as they unfold moment-to-moment is theorized to improve stress-related behavior/physiology through its impact on decreasing depression; yet, one distinctive benefit of MBI may be its potential to offer direct, salutary effects for stress behavior/physiology. MBI may improve identification of cues (e.g., negative affectivity) that prompt behaviors triggered by stress, and to tolerate distress without acting habitually.⁹⁸ MBI also may improve executive function, including the ability to flexibly deploy attention away from cues that prompt stress-behavior and heighten stress physiology.^{59,99}

Figure 1. Theoretical MBI, vs. CBT, effects on depression & insulin resistance by decreasing (a) depression, (b) stress physiology, and (c) stress-related behavior

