6.2.6 Follow-up Visits

There are two follow-ups for this study: a 6-week/post-treatment follow-up and a 1-year follow-up. The 6-week follow-up visit ideal window will be within 4 weeks of the last group session; the 6-week follow-up will be completed no longer than 8 weeks after the last session of the group intervention. The 1-year follow-up visit ideal window will be 12 months (-/+ 4 weeks) after the first group session; the 1-year follow-up will be completed no longer than 18 months after the first day of the group intervention.

The following assessments will take place at each follow-up:

6-week Follow-up Visit

The following assessments that were collected at baseline will be repeated:

- BMI: height/weight body measurements
- Physical: blood pressure/waist circumference (no Tanner/pubertal staging)
- Body composition: BodPod
- Depression symptoms: CES-D survey
- Suicidality/self-harm: K-SADS-COMP interview to assess suicidality and self-harm only since the group program started
- Insulin resistance: OGTT
- Hedonic eating: EDE interview, EES-C, REDS, and laboratory test meal and food preference questionnaire
- Stress reactivity: Trier Social Stress Test
- Therapeutic mechanisms: MAAS, FFMQ, BRIEF-Parent Version, Children's Automatic Thoughts Scale, and PES
- Medical health history: Medical health, including treatment history (e.g., new medications, initiation of counseling, etc.), will be updated
- At-home collection: Adolescents will re-wear ActiGraph assessment of physical activity and repeat home saliva collection

In addition to the repeat assessments, we also will conduct the following evaluations at the post-treatment/6-week follow-up interval:

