8.6.2 Secondary Analyses

One goal of the secondary analyses is to assess for a signal of a clinically significant effect of the interventions on depression and insulin sensitivity, which would be important outcomes in a larger efficacy trial. For these analyses, we will follow the approach of Cocks and Torgesen,¹⁷⁸ in which one-sided 80% CI's are calculated for the treatment effect. If the appropriately powered pilot study does not show evidence of an effect, this does not necessarily preclude the main trial going forward. Careful consideration for the possible reasons for the lack of effect and regarding how the intervention can be strengthened are needed. However, powering a pilot study in this way ensures that it provides as much information as possible. Given our final sample size after accounting for attrition, the pilot study is powered to detect a standardized effect size of 0.3, which is considered a small to medium effect size.

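### The only insulin-sensitivity model described adjusts for change in adiposity, measured after randomization, and the plan does not say which model supplies the one-sided 80% confidence limits

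*Combined protocol and SAP*

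**What the plan says.** Section 8.6.2 has two parts. The first sets a goal to "assess for a signal of a clinically significant effect of the interventions on depression and insulin sensitivity", using one-sided 80% confidence intervals for the treatment effect. It gives a standardized effect of 0.3 as the detectable size, but names no model and no covariates for those intervals.

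The second part covers predictors, mediators and moderators, and describes mixed models for depression, insulin resistance, stress-related behavior and stress physiology. On their content it says: "The models will contain terms for group, time, and a group by time interaction". On covariates: "We will adjust for the baseline value of the outcome, and will also consider adjustment for baseline age, sex, race/ethnicity". It then states, without qualification: "Models will be adjusted for baseline adiposity and change in adiposity". The same sentence gives the reason: "to examine whether decreases in depressive symptoms improves insulin sensitivity independent of adiposity".

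The follow-up lists in section 6.2.6 include "Body composition: BodPod" at both 6 weeks and 1 year, so change in adiposity is observed after assignment. Section 8.6.1 says that covariates will not be used, but only for the Aim 1 and Aim 2 primary analyses. It does not supply an unadjusted insulin-sensitivity model.

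**The concern.** A covariate measured after randomization can itself be a result of the assigned arm. Conditioning on it removes whatever part of the effect runs through it, and randomization no longer protects the comparison from common causes of the covariate and the outcome.

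An arm effect on adiposity is plausible from the protocol's own background. Among the routes by which the mindfulness arm may act, section 2.2 lists "c) lessen stress-related behavior such as hedonic eating", together with physical inactivity. Section 2.1 describes obesity as contributing to insulin resistance. Section 2.1 also says that puberty raises insulin resistance, yet pubertal stage is not among the listed covariates.

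What is at stake is the signal of effect that is meant to inform a larger trial. There is also a knock-on effect. Moderation tests depend on finding significant between-group differences, and mediation tests on there being an improvement to explain. A conditional estimate could therefore decide whether they are run.

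**Working it through.** **The plan's own figure.** The 0.3 is not in dispute here. It cannot be uniquely reproduced, because section 8.6.2 states neither the final sample size nor the power. Read as a confidence-interval criterion it is met: the one-sided 80% half-width is 0.8416 × √(2/n), which equals 0.3 at n = 2 × 0.8416² / 0.3² = 15.7 per arm. At 32 per arm (4 clusters of 8, section 8.2) it is 0.8416 × √(2/32) = 0.210. With the section 8.2 ICC, the design effect is 1 + 7 × 0.06 = 1.42 and the half-width is 0.210 × √1.42 ≈ 0.251.

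**Inputs for the estimand check.** All are assumptions, since the documents give none:
- T = 0.30 SD, the total arm effect on insulin sensitivity, set equal to the plan's detectable size.
- a, the arm effect on change in adiposity: 0 to −0.3 SD.
- b, the effect of adiposity change on insulin sensitivity: −0.2 to −0.6 SD per SD.

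**No common cause.** In a linear model the adjusted arm coefficient is T − a × b. For example, with a = −0.3 and b = −0.6 it is 0.30 − 0.18 = 0.12.

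| a | b = −0.2 | b = −0.4 | b = −0.6 |
|---|---|---|---|
| 0 | 0.30 | 0.30 | 0.30 |
| −0.1 | 0.28 | 0.26 | 0.24 |
| −0.2 | 0.26 | 0.22 | 0.18 |
| −0.3 | 0.24 | 0.18 | 0.12 |

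Simulation with 1,000,000 records per scenario agrees for b = −0.2 and −0.4: for example 0.260 and 0.220 at a = −0.2. The model without change in adiposity returned 0.297 to 0.303 in every scenario. If an arm raised adiposity, the shift would go the other way: a = +0.1 and b = −0.4 give 0.30 + 0.04 = 0.34.

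**With a common cause.** Let an unmeasured factor raise adiposity change by u and lower insulin sensitivity by u, with adiposity change scaled to unit variance within arm. The fitted slope becomes b − u², so the arm coefficient is T − a × (b − u²). With b = −0.4 and u = 0.3 the slope is −0.49:
- a = −0.2: 0.30 − 0.098 = 0.202 (simulated 0.204), against a direct effect of 0.22.
- a = −0.3: 0.30 − 0.147 = 0.153 (simulated 0.152), against a direct effect of 0.18.

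If the factor moves both variables in the same direction, the slope is −0.4 + 0.09 = −0.31. The results are then 0.30 − 0.062 = 0.238 and 0.30 − 0.093 = 0.207, on the other side of the direct effect. The direction of this bias cannot be known in advance.

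**Effect on the signal.** The plan does not state a decision rule. Assume that a signal means a lower 80% limit above zero, and that both models have the same standard error. With the clustered half-width of 0.251, T = 0.30 gives a lower limit of 0.049. An adjusted value of 0.22 gives −0.031, and 0.12 gives −0.131.

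**The stated question.** The purpose concerns decreases in depressive symptoms. The listed terms are group, time, their interaction, the baseline outcome, possible baseline demographics, and adiposity. Change in CES-D is absent, so the adjusted arm coefficient does not directly answer that question.

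**The case against.** The adjustment has a declared mechanistic purpose, and the sentence can be read as an extra model for that one question, added to the model described just before it. Section 2.2 relates the proposed behavioral and physiological pathways to insulin resistance independently of obesity, and reports the earlier CBT trial's effects as independent of body fat change. Adiposity is not named as a mediator in section 8.6.2. The programs involve about six contact hours and do not aim at weight loss, so the arm effect on adiposity may be near zero, in which case the two models agree. Tanner staging is recorded at baseline and at 1 year, so puberty need not be an unmeasured confounder. Section 8.6.2 also says that the trial is not an efficacy study, and that a missing signal need not stop the larger trial.

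All of this stands, and it limits the point. A reader might infer that the 80% limits will be biased, or that adiposity lies on the sponsor's hypothesized pathway. The documents support neither. The intervals are not tied to the adjusted model, and mediation through adiposity is an inference from the eating and activity targets. Nor do the documents say that a pilot effect size will be used to size the next trial.

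What remains is that the wording is definite, whereas age, sex and race/ethnicity are only to be considered, and no insulin-sensitivity model is set out as free of the term.

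**Conclusion.** The point holds in a limited form. The plan leaves the source of its effect signal undefined, and the adjustment that it states as definite conditions on a variable measured after randomization. If that model supplies the intervals, its arm coefficient is not the intention-to-treat effect, and it can be confounded in either direction. Over the assumed ranges, a total effect of 0.30 SD appears as 0.12 to 0.30 SD before any confounding. The upper end applies when the arms leave adiposity unchanged. These figures rest on assumed values and a linear model without an arm-by-adiposity interaction; they illustrate the problem and do not predict this trial's result. The point should be corrected before analysis, but it touches only the secondary analyses.

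**What to change.** In section 8.6.2, state that the one-sided 80% intervals for depression and insulin sensitivity come from the mixed model with arm, time, arm × time and baseline covariates only: baseline outcome, baseline adiposity, and the stratification factors sex and age group. Site can be handled as already planned. Leave change in adiposity out of this model.

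Keep the model with change in adiposity as a labelled exploratory mechanistic analysis. Add change in CES-D to it, so that it addresses its stated question, and state its assumption of no unmeasured confounding.

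The cost is SAP wording and one extra model run. No sample size and no data collection change.
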